11.2 Sample Size Considerations

This is a feasibility study to refine trial logistics. No sample size calculations are being performed.

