POC Point-of-Care Veritor COVID-19 Test

PREDICT Pragmatic Return to Effective Dental Infection Control through Triage and

Testing

PS Project Scientist, NIDCR, NIH

QA Quality Assurance
QC Quality Control
QoL Quality of Life

РΟ

SAE Serious Adverse Event/Serious Adverse Experience

SOP Standard Operating Procedure

UP Unanticipated Problem

US United States

WHO World Health Organization

Expiration Date:

PROTOCOL SUMMARY

Title: Pragmatic Return to Effective Dental Infection Control through Triage and

Testing

Précis: We will conduct a feasibility study to develop and test out procedures for

improved triage and COVID-19 testing of patients in dental practices to improve patient safety. This is one of several feasibility studies to be conducted in Rutgers dental clinics and in dental offices which participate in the National Dental Practice Based Research Network (PBRN). These studies will assess the feasibility of implementing COVID-related

procedures in the dental setting and may provide preliminary data to inform

a larger network-wide study grant application.

Objectives: Primary: The primary objective of this study is to determine patient

willingness to participate in a study and to test survey instruments and logistics developed for a NIH clinical study evaluating the impact of COVID-

19 testing and enhanced triage in dental offices.

Population: This study will take place at Rutgers University School of Dental Medicine.

Up to twenty (20) patients will be recruited in the Rutgers School of Dental Medicine's dental clinics. Only adults who are patients who are scheduled

for dental appointments will be recruited.

Number of Sites: One (1)

Description of Lab-processed saliva tests (Viral PCR SARS-CoV-2 tests) will be

administered to patients coming to the school for care. In addition, the use

of pulse oximeters will be added to the patient COVID-19 symptom triage

protocol.

Study Duration: Twelve (12) months

Subject Participation

Duration:

Intervention:

[figure not shown]
Two (2) weeks.

Estimated Time to Complete Enrollment:

Six (6) months

Expiration Date:

Schematic Study Design for Patient Subjects:

Expiration Date:

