3 OBJECTIVES AND OUTCOME MEASURES

3.0 Rutgers Feasibility Study Outcomes

PILOT Objectives	Brief Description/Justification of Outcome Measure	Outcome Measured By	Time Frame
To Determine Patient Willingness to Participate	Willingness to participate is important in determining whether patients would be willing to participate in a large-scale study	Ratio of patients agreeing to participate as compared to all patients asked to participate Thoroughness of consent process and ability to ask questions	Willingness to Participate: Patients – at time of consent by patients Patients – at End-of-Study
To Determine Patient Willingness/Ability to Follow Thru with Triage, Testing and Survey Administration Procedures	Determining willingness and ability to follow thru with triage, testing and survey administration procedures is important for refining the survey procedures	% who complete the study % who complete surveys o Pre-Visit Patient Survey o End-of-Visit Patient Survey % who feel testing (Saliva procedure was easy to comply with o Specimen collection o Specimen preparation for shipping o Specimen storage o Timeliness of results o Reporting of results	% Complete Study: Patients – End-Of-Visit (Day 1) % All Surveys Completed: Patients – End-Of-Visit (Day 1) % Feel Testing Protocol was Easy to Comply With: Patients – End-Of-Visit (Day 1)
To Determine Ease of Use with REDCap Survey Instruments Patient Subject Start-of-Visit Survey End-of-Visit Survey Triage Survey	Determining the ease of use and completeness of the REDCap instruments enables refinement of the system	% who feel surveys are easy to complete due to administration method:	% indicating surveys were easy to complete due to administration method: • Patients – at end of patient visit % indicating survey questions were easy to understand: • Patients – End-Of-Visit (Day 1) % Surveys Completed: • Patients – End-Of-Visit (Day 1)

3.1 Primary Outcomes for Full Study (Data Collection is Being Performed to Determine Instrument Feasibility)

Full Study Objective	Brief Description/Justification of Outcome Measure	Outcome Measured By	Time Frame

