4 STUDY DESIGN

Description: This study will assess the feasibility of implementing one COVID-related testing procedure in the dental setting. Results from this study may provide preliminary data to inform a larger network-wide study grant application.

Study Population: The study population for this study will be patients seen at the Rutgers School of Dental Medicine.

Important Outcomes: For this study, important outcomes include percent of patients willing to participate and percent completing the protocol.

Single or Multicenter: Single- this study will utilize the Rutgers School of Dental Medicine's Newark facility.

Number of Study Groups/Arms: One (1)

Expected Duration of Subject Participation: Subjects will be actively participating in the study for 2 weeks.

Sequence of Procedures and Duration of Study Period: Consent Process

About two weeks prior to their scheduled dental visit, patients will be contacted by the dental office to determine their willingness to participate in the study. Patients who indicate interest will be sent an email link, which opens the consent. The consent will clearly outline participant expectations and offer the opportunity for potential participants to contact the office for more information as needed. Participants who fully understand the study and elect to participate will affirm their willingness to participate by clicking the "I agree to take part in this study" button at the end of the consent form. Once in the office to provide their saliva sample, patients will also be asked to provide signed informed consent.

Study Procedures

Study participants will be asked to do the following:

- Two weeks before the dental visit
 - o Complete an electronic survey: Patient Pre-Visit Survey
 - Questions explore perceptions of safety and comfort, reasons for delaying dental care, concerns about returning to dental care, safety precautions valued, importance of triage and testing, and demographics
 - Launched automatically after the completed consent
 - Receive a saliva collection kit by mail
- One week before the dental visit
 - o Complete a COVID-19 saliva test
 - Spit into a tube
 - Package as directed
 - Drop off the completed test kit at the dentist's office
- Day prior to the dental visit
 - Undergo a COVID-19 triage screening over the phone*
 - Screening includes symptom questions (presence or absence of):
 - fever or chills
 - cough
 - shortness of breath or difficulty breathing
 - fatigue
 - muscle and body aches

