5.3 Strategies for Recruitment and Retention

Target Sample Size: 20 patients.

Target Sample Size by Gender, Race, Ethnicity, and Age: Study population will be drawn from patients at the Rutgers School of Dental Medicine. It is estimated that about ½ will be female, ½ male. All will be English speaking. Age range will be between 18 and 100 years of age. Racial and ethnicity background will be reflective of the respective populations at the Rutgers Schools of Dental Medicine with about 52% being African American and 33% Hispanic.

Study Population: The patient study population will be drawn from outpatient dental clinics located at Rutgers University School of Dental Medicine.

Inclusion of Women and Minorities and Individuals of All Ages:

Women: Women will be included in this study. Pregnant women are eligible to participate.

Minorities: Minorities will be included in this study.

Recruitment Strategies: Patients treated in the Rutgers School of Dental Medicine's Oral Medicine clinic will be recruited. If 20 patients cannot be recruited in the Oral Medicine clinic, recruitment will expand to the school's other clinics. It is not anticipated that there will be difficulties recruiting sufficient patients.

Retention: In order to minimize loss of study participants and/or incomplete data collection, the following activities will take place:

- The Research Clinical Director will work with the co-investigators responsible for recruiting subjects and completing surveys.
- Participants will receive compensation.

Compensation and Scheduled Payments: Patients who complete the protocol, including the post-visit survey will be provided \$100.

Additional Plans to Minimize Loss of Follow-up and Missing Data: The following will minimize loss of follow-up and/or missing data:

• When appropriate, REDCap survey data fields are set to "required".

REDCAP validation rules on data fields to limit responses to valid responses

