11 STATISTICAL CONSIDERATIONS

11.1 Study Hypotheses.

For this study, we hypothesize:

- Patients in offices with PBRN dentists and hygienists will be willing to participate
- Surveys will be easy to complete
- Testing protocols will be easy to complete

Analyses will be performed to test these hypotheses.

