11.3 Final Analysis Plan

Data to be collected includes:

Item	Type of Variable
Willingness to Participate	 Willingness to participate (Binary – Yes/No)
Patient willingness to participate	
Triage Survey	Ease of Administration (3 point Likert Scale) Very easy to complete survey due to administration method Easy to administer complete survey due to administration method Not easy to complete survey due to survey administration method Completeness (Binary – Yes/No) Question understandability (3 point Likert Scale) Very clear to understand Understandable with some clarification provided by the administrator Not clear to understand
Safety Perception Survey	
Start-of-Visit Patient Survey End-of-Visit Patient Survey	Administration method (3 point Likert Scale) Very easy to complete survey due to administration method Easy to complete survey due to administration method Not easy to complete survey due to administration method
	 Completeness (Binary – Yes/No)
	 Question understandability (3 point Likert Scale) Very clear to understand Understandable with some clarification provided by the administrator Not clear to understand
Testing Logistics	Specimen Collection (3 point Likert Scale)
LAB – saliva SARS-CoV-2 viral test	 Very easy to collect Easy to collect Not easy to collect Specimen preparation for shipping (3 point Likert Scale) Very easy to prepare Easy to prepare Not easy to prepare Specimen storage (Binary – Easy/Not Easy) Easy to Store Not easy to store

	Timeliness of results (3 point Likert Scale) Very timeless access to results Timely access to results Access to results not timely Reporting of results (3 point Likert Scale) Very easy to access results Easy to access results Not easy to access results	
Testing Case Report	 Completeness (Binary – Yes/No) 	

Descriptive statistics (frequencies) for all variables will be analyzed.

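### Sections 11.2 and 11.3 give no precision statement and no confidence intervals, so the feasibility proportions would be reported without their uncertainty

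*Combined protocol and SAP*

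**What the plan says.** Section 11.1 hypothesises that patients will be willing to take part and that the surveys and the testing procedures will be easy. It adds: "Analyses will be performed to test these hypotheses". No test, level or success criterion follows.

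Section 11.2 gives the purpose as improving logistics and states "No sample size calculations are being performed". It says nothing about how precisely the sample will estimate anything. Section 11.3 lists binary and three-point items and ends with "Descriptive statistics (frequencies) for all variables will be analyzed". It names no interval and no confidence level. Section 15.4 refers to a Section 12.4 for the data analysis, but Section 12 concerns source documents and has no such subsection.

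On what the study is for, Section 4 says "important outcomes include percent of patients willing to participate and percent completing the protocol" and "Results from this study may provide preliminary data to inform a larger network-wide study grant application". Section 3.0 measures willingness as "Ratio of patients agreeing to participate as compared to all patients asked to participate" and justifies it by its bearing on a large-scale study.

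On size, Section 5.3 has "Target Sample Size: 20 patients". The Protocol Summary makes 20 a ceiling, and Section 5.4.2 rules out replacing patients who withdraw.

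**The concern.** The main products of this study are proportions: agreeing to take part, completing the study and the surveys, and finding the surveys and testing easy. Section 11.1 promises to test hypotheses about willingness and ease, and Section 3.0 uses willingness to judge what would happen in a larger study. Both are statements about patients beyond those observed. A frequency table alone supports neither.

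A reader of a later application could see a completion figure of 90% with no sign that, from 20 patients, it is compatible with a true value of about two thirds.

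**Working it through.** The plan states no power, precision or derived sample size, so there is no figure of its own to reproduce. The check asks what precision the stated numbers imply.

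**Inputs from the documents.** At most 20 patients enrolled (Protocol Summary, Section 5.3); withdrawals not replaced (Section 5.4.2); willingness divided by all patients asked, number not stated (Section 3.0).

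**Assumptions not in the documents.** A two-sided 95% level; the observed counts shown; all 20 patients analysed unless noted; for willingness, 20 patients agreeing and the number asked treated as fixed.

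**Formulas**, for x successes in n with p = x/n and z = 1.96:

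- Clopper-Pearson: lower limit = 2.5% quantile of Beta(x, n − x + 1); upper limit = 97.5% quantile of Beta(x + 1, n − x). When x = n, the lower limit is 0.025^(1/n) and the upper limit is 100%.
- Wilson: [p + z²/2n ± z·√(p(1 − p)/n + z²/4n²)] / (1 + z²/n).

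**Example, 20/20, exact.** 0.025^(1/20) = 0.832, so 83.2% to 100%.

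**Example, 18/20, Wilson.** z²/n = 0.192. Centre = (0.900 + 0.096)/1.192 = 0.836. Half-width = 1.96·√(0.0045 + 0.0024)/1.192 = 0.137. The interval is 69.9% to 97.2%.

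**Completion and ease, all 20 analysed**

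| Observed | Exact 95% interval | Half-width (points) | Estimate to farther limit (points) |
|---|---|---|---|
| 10/20 = 50% | 27.2-72.8% | 22.8 | 22.8 |
| 14/20 = 70% | 45.7-88.1% | 21.2 | 24.3 |
| 16/20 = 80% | 56.3-94.3% | 19.0 | 23.7 |
| 18/20 = 90% | 68.3-98.8% | 15.2 | 21.7 |
| 20/20 = 100% | 83.2-100% | 8.4 | 16.8 |

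Wilson limits are slightly narrower: the half-width is 20.1 points at 10/20 and 13.7 at 18/20.

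**Fewer analysed, exact.** 8/16 = 50% has a half-width of 25.3 points, and 12/15 = 80% has an interval of 51.9-95.7%. This matters most for the ease items, which a patient who has left cannot answer. Study completion can keep all enrolled patients as its denominator.

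**Willingness, 20 agreeing, exact**

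| Asked | Estimate | 95% interval | Half-width (points) |
|---|---|---|---|
| 25 | 80% | 59.3-93.2% | 16.9 |
| 40 | 50% | 33.8-66.2% | 16.2 |
| 50 | 40% | 26.4-54.8% | 14.2 |
| 100 | 20% | 12.7-29.2% | 8.3 |

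**The case against.** The strongest reply is that a feasibility study aimed at logistics needs no sample size calculation, and that frequencies are counts from which any reader can derive an interval. The first half stands: omitting a power calculation and choosing 20 are not errors. The second half stands only in part. A count with a clear denominator is enough to compute an interval, but the number asked is not stated in advance, and Section 11.3 gives no cut-point for the three-point ease items. A plan that promises to test hypotheses should not leave the inference to the reader.

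Three stronger readings are tempting, and the documents do not support them.

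- A reader might infer that every key proportion rests on at most 20 patients. Willingness does not: its denominator is everyone asked, and at 100 asked the half-width is about 8 points.
- A reader might take 15 to 23 points as the possible error. That is the exact half-width for 90% down to 50% of 20 patients. The intervals are asymmetric, so it is not a bound: 14/20 lies 24.3 points above its lower limit.
- A reader might infer that the network study will be planned on these percentages. The protocol says only that results may inform an application, describes this as one of several feasibility studies, and justifies the completion and ease outcomes as refining survey procedures and the REDCap system.

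**Conclusion.** The point holds as a gap in reporting and precision. No section plans an interval or states an expected precision, while Section 11.1 promises inference and Section 3.0 looks to a large-scale study. Under the assumptions listed, a completion or ease result from 20 patients would have exact 95% limits of 27-73% at an observed 50%, 56-94% at 80%, 68-99% at 90% and 83-100% at 100%. Wilson limits are slightly narrower, and either kind widens if fewer patients are analysed. The precision of willingness cannot be fixed in advance, because it depends on how many are asked.

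The consequence for a larger study is possible rather than established. The planned description is not invalid; it is incomplete for the use the protocol names. The change is worth making because it costs almost nothing.

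**What to change.** In Section 11.3, report each of the following with its numerator, denominator and a 95% interval, naming the method (exact or Wilson) in advance:

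- willingness, over all patients asked;
- study completion;
- survey completion;
- each ease proportion, after stating how the three-point items are split, for example the two favourable categories against the unfavourable one.

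In Section 11.2, add a sentence on the precision that 20 patients give for completion and ease, for example about ±23 points at an observed 50% and limits of 68-99% at an observed 90% (exact 95% limits, all 20 analysed). Say that the precision of willingness will depend on the number asked.

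This takes a few sentences and trivial analysis work. No extra patients are needed, and this protocol need not commit the network study to any planning rule. The downside is that the reported figures will look less certain. The text should also say that the intervals cover sampling error only: patients come from one dental school, recruited from its Oral Medicine clinic before any other, with $100 paid on completion, so the limits do not bound what would happen in network practices.

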11.3 Final Analysis Plan

Data to be collected includes:

Item	Type of Variable
Willingness to Participate	 Willingness to participate (Binary – Yes/No)
Patient willingness to participate	
Triage Survey	Ease of Administration (3 point Likert Scale) Very easy to complete survey due to administration method Easy to administer complete survey due to administration method Not easy to complete survey due to survey administration method Completeness (Binary – Yes/No) Question understandability (3 point Likert Scale) Very clear to understand Understandable with some clarification provided by the administrator Not clear to understand
Safety Perception Survey	
Start-of-Visit Patient Survey End-of-Visit Patient Survey	Administration method (3 point Likert Scale) Very easy to complete survey due to administration method Easy to complete survey due to administration method Not easy to complete survey due to administration method
	 Completeness (Binary – Yes/No)
	 Question understandability (3 point Likert Scale) Very clear to understand Understandable with some clarification provided by the administrator Not clear to understand
Testing Logistics	Specimen Collection (3 point Likert Scale)
LAB – saliva SARS-CoV-2 viral test	 Very easy to collect Easy to collect Not easy to collect Specimen preparation for shipping (3 point Likert Scale) Very easy to prepare Easy to prepare Not easy to prepare Specimen storage (Binary – Easy/Not Easy) Easy to Store Not easy to store

	Timeliness of results (3 point Likert Scale) Very timeless access to results Timely access to results Access to results not timely Reporting of results (3 point Likert Scale) Very easy to access results Easy to access results Not easy to access results	
Testing Case Report	 Completeness (Binary – Yes/No) 	

Descriptive statistics (frequencies) for all variables will be analyzed.

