 - headache
 - loss of taste

[figure not shown]
- loss of smell
- sore throat
- congestion or runny nose
- nausea or vomiting
- diarrhea
- At the start of the Dental Visit
 - Undergo a COVID-19 triage screening in the office*
 - Screening includes symptom questions, temperature check, and pulse oximeter reading
- At the End of the Dental Visit
 - Complete two electronic surveys
 - Patient End-of-Visit Survey
 - Questions explore perceptions with testing preferences, PPE observed, environmental controls observed, concerns about returning to dental care, safety precautions valued, importance of triage and testing, likelihood of reporting symptoms, dentists role in COVID-19 testing and vaccinations
 - Patient Participation Survey
 - Questions explore perceptions related to study participation including survey and testing logistics

If any aspect of the COVID-19 triage screening is positive, appointment will be postponed and the participant will be referred to their primary care physician for further testing.

- A Positive screening by reporting one or more symptoms
- A positive temperature is considered greater than 100.4 degrees F
- A positive pulse oximeter is considered when the blood oxygen saturation level is below 95%

The results of the lab processed COVID-19 test will be reported to the Clinic Director or one of the coinvestigators by the lab prior to the scheduled dental visit. Results will be recorded in the *Testing Case Report* form in REDCap.

- If **POSITVE**: The Clinic Director or one of the co-investigators will communicate positive results to the participant upon receipt. Positive participants will be instructed to consult with their primary care provider for further testing.
- If NEGATIVE: The Clinic Director or one of the co-investigators will communicate negative results to
 the participant by phone on the day prior to the dental visit after the COVID-19 triage screening is
 performed.

Methods for Data Collection

REDCap will be used to collect and maintain all study data. For all surveys and case reports, the Research Clinical Director or co-investigator will enter data directly into REDCap. Surveys will be entered by the patient with the Clinical Director or co-investigator's assistance.

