7.1 Study Procedures/Evaluations

The following study procedures will be completed:

Patient Subjects - LAB Protocol

Procedure and Evaluations	Purpose	Completed as Part of Study	When Performed	How Completed
Obtain Informed Consent	Complete informed consent	Yes	2 Weeks Prior (day- 14 +/-7 days) 1 Week Prior (day-7 +/-5 days)	Electronic consent obtained prior to initiating Pre-Visit Patient Survey Electronic signatures collected via REDCap Informed Consent Form when saliva specimen brought to office
Triage Case Reports	Collect COVID-19 screening data	Yes	Day Prior (day -2 +/- 2 days) Visit (day 1)	Data entered into REDCap via eCRF by Clinical Director, co-investigator or study staff member who interviews subject
Testing Case Reports	Collect information on outcomes of COVID-19 testing		Day Prior (day -2 +/- 2 days	Saliva Viral SARS-CoV-2 test results entered into REDCap via eCRF by Research Clinical Director, coinvestigator or study staff member based on testing result report obtained from secure e-mail.
Start-of-Visit Patient Survey Safety and Comfort COVID-19 Testing Preferences Perception of Importance Medical history Likelihood to report COVID-19 symptoms	Collect outcome measures	Yes	Visit (day 1)	Data entered via REDCap self- administered survey.
Dental Procedures Performed	Maintain patient oral health	NO	Visit	Completed by Dental Health Care Workers
PPE observed in office Environmental controls observed in office	Collect outcome measures	Yes	Visit (day 1)	Data entered via REDCap self- administered survey.
Patient Participation Questionnaire	Collect feasibility information on surveys and logistics	Yes	End of Study (Day 28)	Data entered via REDCap self- administered survey.

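### The middle level of the clarity scale mixes how clear the questions were with whether staff helped, and the plan does not settle which surveys are assisted

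*Combined protocol and SAP*

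**What the plan says.** Section 11.3 lists the same three-level understandability item for the Triage Survey and for the two surveys it names as "Start-of-Visit Patient Survey End-of-Visit Patient Survey". The top level is that the questions were very clear, the bottom that they were not clear, and the middle is "Understandable with some clarification provided by the administrator". The only planned analysis is frequencies. Section 3.0 makes the percentage of patients who found the questions easy to understand a feasibility outcome, under an objective meant to refine the survey system.

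On how surveys are completed, the plan says:

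- Section 4, consent and study procedures: "Patients who indicate interest will be sent an email link, which opens the consent". The Pre-Visit survey, about two weeks before the visit, is "Launched automatically after the completed consent".
- Section 7.1, Start-of-Visit row, timed at Day 1: "Data entered via REDCap self- administered survey". The rows for observed protective equipment and environmental controls, and for the Participation Questionnaire, carry the same entry.
- Section 7.1, triage row: data are entered by the Clinical Director, a co-investigator or a "study staff member who interviews subject".
- Section 4, data collection: "Surveys will be entered by the patient with the Clinical Director or co-investigator's assistance".

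**The concern.** A response level should describe one thing. Take two patients who found the same questions partly unclear. One had staff explain them; the other asked nobody and finished anyway. The first has an exact answer on the scale and the second has none.

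This matters because the response counts are themselves the result. With frequencies only, nothing later in the analysis can separate unclear wording from staff help. The two call for different action before a larger study: rewriting a question, or providing someone to explain it.

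**Working it through.** The plan states no figure for this outcome, so there is nothing to reproduce. The check is of wording and consistency, with one line of arithmetic.

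**Step 1. What the levels can record.** Cross clarity with help:

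| | Staff clarified | No clarification |
|---|---|---|
| Clear throughout | (not needed) | Top level |
| Partly unclear | Middle level | No matching level |
| Not clear | Bottom level | Bottom level |

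One cell has no accurate code: partly unclear, no clarification.

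**Step 2. Where that cell can occur.**

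- Triage: staff interview the patient, so the middle level fits.
- Start-of-Visit survey: self-administered in Section 7.1, assisted under the general sentence in Section 4.
- End-of-Visit survey: Section 7.1 gives self-administered entry for the protective-equipment and environmental items, which Section 4 places in this survey. The same general sentence says assisted.
- Pre-Visit survey: opens automatically from an e-mailed link in Section 4, with no staff contact described at that step. The general sentence makes no exception for it.
- Just before that general sentence, Section 4 also says staff enter the data for all surveys and case reports, which is a third description of mode.

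**Step 3. Which survey Section 11.3 means.** The early survey has two names:

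| Section | Two weeks prior | Day 1, before treatment |
|---|---|---|
| 4 | Pre-Visit | Triage only |
| 6.1 | Pre-Visit | Start-of-Visit and triage |
| 7.1 | Pre-Visit, mentioned only in the consent row | Start-of-Visit and triage |
| Appendix A | Start-of-Visit | Triage only |

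The form list in Section 12 has a Pre-Visit form and no Start-of-Visit form. Section 3.0 uses Pre-Visit under survey completion and Start-of-Visit under ease of use. Section 11.3 uses Start-of-Visit only.

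- If the two names are one instrument (as Section 12 and Appendix A suggest), the scale covers the survey opened from the e-mailed link.
- If they are two instruments (as Section 6.1 suggests), the misfit attaches to the Day 1 survey called self-administered, and Section 11.3 gives the Pre-Visit survey no understandability item.

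Both readings call for a correction.

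**Step 4. Size.** Target n = 20 (Section 5.3). One patient placed in a different level moves a reported percentage by 1/20 = 5 points, and k patients by at most 5k points. The documents give no value for k. If k were 1, 4 or 8, the largest shift in any one level would be 5, 20 or 40 points. That range only restates the assumed k; it is not an estimate. The direction is also unknown. Section 3.0 does not say which levels count as easy to understand: if only the top level counts, only moves into or out of the top matter; if the top two count, only moves into or out of the bottom matter.

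**The case against.** The strongest reply is that help may be available for every survey. The assistance sentence in Section 4 is general. An automatic launch says how a survey opens, not that nobody can help with it. The self-administered entry in Section 7.1 belongs to a Day 1 survey, done where staff are at hand. Section 3.0 times the understandability rating at the end of the visit, so it appears to be given in the clinic and not alone at home. Section 11.3 never names the Pre-Visit survey.

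Much of this stands, and it rules out three stronger readings that a reader might infer:

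- *That the Pre-Visit survey has no administrator.* Section 4 describes none at the launch step, but its assistance sentence exempts no survey. The provision to "offer the opportunity for potential participants to contact the office for more information as needed" concerns the consent, so it does not settle the matter either way.
- *That partly unsure patients are forced into the top or bottom level.* They may choose the middle as the nearest fit. Misclassification is possible, not forced.
- *That a comparison of remote with in-clinic surveys is spoiled.* No such comparison is planned in this single-arm study.

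What does not stand is the idea that assistance cures the wording. Help with entering a survey is not the same as clarifying a question, and a patient with staff nearby may not ask. Rating the survey later, in the clinic, does not change whether clarification was given when it was completed.

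**Conclusion.** The point holds and is minor. The middle level merges clarity with receipt of help, so a partly unsure, unassisted patient has no accurate option and may be recorded in any direction, including as having received help that was not given. This rests on at least one patient being partly unsure and unassisted on a survey that Section 11.3 covers; the documents neither exclude this nor say how often it would happen. Each such patient is worth 5 percentage points at n = 20, and more if fewer respond. The conflicts on survey mode and survey name are plain on the page and need no assumption. Nothing beyond a descriptive feasibility outcome is affected.

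**What to change.** 1. In Section 11.3 and in the instrument, reword the middle option so that it does not depend on how the survey was administered, for example *Mostly understandable, some questions unclear*.
2. Add a separate yes/no item for each survey: did anyone help with or explain the questions?
3. Report clarity by survey, and state in Section 3.0 which levels count as easy to understand.
4. Reconcile Sections 3.0, 4, 6.1, 7.1, 11.3, 12 and Appendix A on the name, timing and mode of each survey, and say whether Start-of-Visit and Pre-Visit are the same instrument. If they are not, state whether the Pre-Visit survey is also rated for understandability.

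The cost is one reworded option, one added item and an editorial correction across sections. Enrolment and sample size are unaffected.
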